There is a theoretical risk of reduced closure of patent ductus arteriosus (PDA) in infants treated with indomethacin who receive carnitine supplementation as opposed to placebo.²⁸ In our previous study, an increase in PDA ligation among infants treated with indomethacin was seen. The observation may have been due to chance. It is also possible that an interaction between carnitine and indomethacin occurred. Indomethacin enhances the process of apoptosis, which mediates PDA closure.⁵³ Carnitine has been shown to reduce apoptosis in such models as ischemia-reperfusion injury.⁵⁴ However, it should also be noted that the group of carnitine-supplemented infants with the increased rate of PDA ligation had lower birthweight and had received more fluids prior to intervention, compared to the infants in the placebo group. Increased fluid intake has been shown to be associated with failure of medical management of PDA.⁵⁵If this effect was in fact associated with decreased apoptosis, it reinforces our hypothesis regarding neuronal protection, a benefit we feel outweighs a theoretical risk of reduced PDA closure.

Despite this incidental finding, there have been no other reports of adverse effects in neonates receiving supplementation doses (approximately 50 µmol/kg/day) although approximately one-third of NICU's in the United States supplement carnitine routinely in parenteral nutrition. In addition, there have been at least 13 clinical trials of carnitine in premature infants which did not report side effects.

We have established a Data and Safety Monitoring Board. The DSMB will meet approximately every 6 months to review safety data. Meetings will be convened via conference calls. Emergency meetings may be convened at any time by the board in the event that questions/concerns regarding patient safety have been raised or if an unexpected AE/SAE occurs that is possibly related to the study. A report will be circulated to the board members approximately 2 weeks before the board meeting in order to provide them with adequate time to review the materials.

Infants in our study will be monitored closely in order to detect unforeseen side effects. All AEs will be collected and recorded as part of the study. For each, the PI will include the following assessments:

- Anticipated/unanticipated
- Relationship to the study intervention
- Outcome

The DSMB will review all adverse events as described in the Charter. All unanticipated problems will be reported to the DSMB and IRB within 5 days of the PI becoming aware of the problems.

With the upcoming revisions in the IRB AE reporting policy, we have decided to not follow the current IRB adverse event reporting policy dated 2008; instead we will report AEs to the IRB as follows:

- 1. Unanticipated Problems defined as anyevent, deviation, or problem
 - thatmeetsallofthefollowingcriteria:
 - unanticipated; AND
 - possibly,probablyordefinitelyrelatedto studyparticipation;AND
 - fatal,life-threatening,orseriousORsuggestsgreaterriskofharmtostudy participant(s)or othersthanwaspreviouslyknownorrecognized
- 2. Deathofaparticipantifitoccurswithin30 daysofadministrationofthestudymedication
- 3. AProtocolDeviation or an incident, experience,oroutcomethatmayplacetheparticipantorothersatgreatermedical, physiological,socialriskoreconomicriskthanwaspreviouslyknownorrecognized
- 4. AnydeviationfromIRBorInstitutionalPolicyorProcedurewhichhasthepotentialto adverselyimpactoneormoresubjectsortheoverallintegrityofdatacollected
- 5. AnyreportingthattheIRBcitesasaconditionofapprovaloftheprotocol
- 6. Complaintfromaparticipantorotherindividualwhenthecomplaintindicates unexpectedrisksorthecomplaintcannotberesolvedbytheresearchteam

- 7. DeviationfromtheIRBInformedConsentPolicy
- 8. Systematicdatacollectionerrors
- 9. Breachofconfidentiality

It is well-known that the very preterm, low birth weight infants included in this study have increased mortality compared to full-term infants. Review of our own Weiler NICU data in 2010 revealed a high mortality rate ininfants less than 30 weeks gestational age: approximately 75% for infants of gestational age of 23 weeks, 24% for gestational age 24-26 weeks, and 5% for infants of gestational age 27 – 29 weeks. Thus, we expect similar rates in infants enrolled in our study.

An additional amount of blood will be drawn as part of the study protocol. The estimated amount of blood is approximately $200 - 300 \mu$ I two to three times over the course of the study. The blood draw will be obtained with other routine bloodwork whenever possible in order to avoid additional discomfort to the infant.

Benefits:

Carnitine has been shown to have anti-oxidant effects, enhance cellular function and prevent apoptosis. Supplementation has been associated with protection of neurons against hypoxic-ischemic injury in both in vitro and in vivo models. In preterm infants, carnitine supplementation is associated with decreased time to regain birthweight. Thus, potential benefits of carnitine supplementation in premature infants include hypoxic-ischemic neuronal injury protection and enhanced brain growth, leading to improved neurodevelopmental outcomes.

Problems with neurodevelopment are a well-known morbidity for infants born very preterm. Thus, it is important from a public health and scientific standpoint to determine whether carnitine supplementation has an impact on this outcome. The potential identification of an important physiological benefit of carnitine could lead to changing current recommendations for nutritional supplementation for preterm infants to include carnitine.

Financial Compensation:

No financial compensation is planned. Carnitine supplementation will not be charged to the patient or insurance company.

References:

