We hypothesize that preterm infants supplemented with early physiologic doses of L-carnitine while on parenteral nutrition will have improved short-term growth parameters and significantly higher neurobehavioral scores when compared with control infants.

Primary Aims:

To determine whether carnitine supplementation is associated with:

- 1. Decreased percent weight loss within the first two weeks of life and decreased length of time to regain birthweight.
- 2. Improved performance on the NICU Network Neurobehavioral Scale (NNNS) at 40 weeks postmenstrual age (+/- 2 weeks).

Secondary Aims:

To determine whether carnitine supplementation is associated with:

- 1. Increased rate of growth of head circumference within the first month of life and increased food efficiency (weight gain/calorie intake) during the supplementation period.
- 2. Normalization of the serum carnitine profile at two weeks of life, compared with infants born at a post-menstrual age 2 weeks later.
- 3. Enhanced brain maturation as measured by amplitude-integrated EEG (aEEG) measurements obtained during the hospital course
- 4. Fewer abnormal findings, better brain growth, white matter development and brain metabolism on brain magnetic resonance imaging (MRI) at 36-40 weeks' corrected age (prior to hospital discharge)

Because of the potential for systemic effects of L-carnitine supplementation, we will also monitor those variables which showed significant difference in our prior study: rates of proven infection, hearing screen failure and PDA ligation.

Primary Outcomes:

- 1. Length of time to regain birthweight,
- 2. Percent weight loss in the first two weeks of life,
- 3. Neurodevelopmental scores on the NICU Network Neurobehavioral Scale (NNNS) at 40 weeks post-menstrual age (+/- 2 weeks)

Methods/Design:

This is a prospective, randomized controlled clinical trial involving infants with gestational age (GA) <32 wks who are born at either the Jack D. Weiler Hospital or the Wakefield Division of Montefiore and admitted to theirNeonatal Intensive Care Unit. Informed consent will be obtained from the parents of eligible patients as early as possible within 72 hours of birth. Infants whose parents have signed an informed consent form will be randomized to receive either carnitine supplementation (50 µmol/kg/day) versus placebo within 72-96 hours of birth.

Inclusion criteria:

- Infants born <32weeks' gestation
- Exclusion criteria:
 - Presence of

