Study supplementation: Infants randomized to the treatment group will receive 50 µmol/kg/day of Lcarnitine intravenously for 2 weeks, and infants randomized to placebo will received 5% glucose, similar volume to the L-carnitine group. At two weeks, sufficient carnitine is provided in enteral feeds of either breast milk or infant formula. If no intravenous access is available before the supplementation endpoint, the equivalent dose of enteral study supplement (L-carnitine or placebo) will be administered.⁴¹ Parenteral and enteral nutrition will be provided according to standard NICU protocol.

Of note, as many as 10% of the infants in the study will likely continue to rely primarily on parenteral nutrition beyond the proposed two-week supplementation period. Enteral feeds may be withheld from these infants due to underlying illnesses such as sepsis or gastrointestinal disorders like necrotizing enterocolitis. Due to the presence of underlying illness, these infants are at an even higher risk for developing developmental delays.⁴²Therefore, in study patients who are not receiving adequate enteral nutrition (100 cc/kg/day of enteral intake) after 2-weeks of study supplements, carnitine supplementation will be continued until these infant are receiving adequate enteral feeds; at this point, their physiologic carnitine requirements will be met by enteral nutrition alone.

Timeline of Assessments:

- a. Within 72 hours of birth
 - i. Patient enrollment and initiation of study protocol

- ii. Initial carnitine panel drawn
- iii. Initial aEEG reading obtained within 2-3 days of study initiation
- iv. Study Supplement begins within 72-96 hours of birth
- b. Two weeks after study initiation
 - i. Study Supplement concludes (in a small sub-set of patients, study supplementation will be continued until enteral feeds reach 100 cc/kg/day)
 - ii. Follow-up carnitine panel drawn (in addition, as blood transfusions may impact carnitine levels, serum carnitine profiles will be drawn prior to blood transfusion administered between the first and second weeks of life)
- c. aEEG readings will be obtained within 2-3 days of study initiation and at the following post-menstrual ages: 28 weeks (if infant <27 weeks at birth), 32 weeks', 36 weeks', and at 40 weeks' (if infant is still admitted to the NICU).
- d. 36-38 weeks' corrected age
 - i. Cranial MRI
- e. 40 weeks GA (+/- 2weeks)
 - i. Neurodevelopmental assessment

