- f. Neurodevelopmental assessment at 18-24 months corrected age
 - i. Bayley Scales of Infant and Toddler Development III (BSID-III)
 - ii. Modified Checklist for Autism in Toddlers (M-CHAT)
 - iii. Child Behavior Checklist (CBCL)

Individual Infant Timeline:

 2. Study supplement given (within 24 hours of enrollment for total 2 weeks or until enteral intake is at 100 cc/kg/day) 3. Data collection throughout the NICU course (Growth parameters, fluid and nutrition intake and important hospital events), also includes interview with mother to record demographic information and maternal characteristics 4. Blood carnitine panels – drawn at study enrollment and at the end of the intervention (and again if a blood transfusion is administered within this period) 5. Amplitude-integrated EEG readings – within 2-3 of study enrollment and at 28, 32, 36 and 40 weeks' post-menstrual age (dashed lines) 6. Hearing screens – OAE and BAER during the NICU course 7. Brain MRI at 36-40 weeks' GA 8. NNNS at term-equivalent follow-up visit 	1	Study Enrollment (within 72 hours of birth)	Birth	
 24 hours of enrollment for total 2 weeks or until enteral intake is at 100 cc/kg/day) 3. Data collection throughout the NICU course (Growth parameters, fluid and nutrition intake and important hospital events), also includes interview with mother to record demographic information and maternal characteristics 4. Blood carnitine panels – drawn at study enrollment and at the end of the intervention (and again if a blood transfusion is administered within this period) 5. Amplitude-integrated EEG readings – within 2-3 of study enrollment and at 28, 32, 36 and 40 weeks' post-menstrual age (dashed lines) 6. Hearing screens – OAE and BAER during the NICU course 7. Brain MRI at 36-40 weeks' GA 8. NNNS at term-equivalent follow-up visit 				0 hours
 3. Data collection throughout the NICU course (Growth parameters, fluid and nutrition intake and important hospital events), also includes interview with mother to record demographic information and maternal characteristics 4. Blood carnitine panels – drawn at study enrollment and at the end of the intervention (and again if a blood transfusion is administered within this period) 5. Amplitude-integrated EEG readings – within 2-3 of study enrollment and at 28, 32, 36 and 40 weeks' post-menstrual age (dashed lines) 6. Hearing screens – OAE and BAER	2.	24 hours of enrollment for total 2 weeks		72 hours

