- 1. Patient demographics: date of birth, birth weight, gestational age as determined by best obstetric estimate or Ballard score, SGA or LGA status, Apgar scores, birth history, delivery room management, gender, ethnicity.
- 2. Maternal characteristics: maternal age, maternal language, ethnicity, presence of prenatal care, type of insurance coverage, maternal educational status, presence of maternal depression, teratogen exposure (alcohol, tobacco or illicit drug use during pregnancy), antenatal steroid use, hypertension/pre-ecclampsia, gestational diabetes/Type I or II diabetes, and maternal infections.
- 3. Management of fluid and nutrition: daily fluid intake and urine output, glucose infusion rate, total caloric intake, total protein intake, and food efficiency (weight gain divided by caloric intake) while on study supplement.
- 4. Hospital course:
 - a. Growth parameters: weight, length and head circumference at birth, daily weight until birthweight regained and then weekly, weekly length, and head circumference two times per week for four weeks)
 - b. Cardiovascular: need for vasopressors, presence of PDA (including medical or surgical treatment; platelet count and mean fluid intake at time of treatment)
 - c. Gastrointestinal: feeding intolerance, NEC, presence of gastrointestinal reflux,
 - Neurological: results of aEEG readings, results of head ultrasounds including presence of germinal matrix/intraventricular hemorrhage and periventricular leukomalacia, cranial MRI results
 - e. Opthalmological: grade of retinopathy of prematurity and treatment or ophthalmologic diagnosis,
 - f. Hematologic: transfusion history including dates
 - g. Infectious disease: presence of concurrent presumed and proven infection,
 - h. Other: performance of any surgical procedures, duration of intravenous access, use of medications, and hearing screen results (OAE and/or ABR) with observed thresholds of hearing frequencies.
 - i. Clinical Risk Index for Babies (CRIB) scores will be calculated for each infant.
 - j. We will also monitor for possible short-term side effects.
- 5. Discharge information: weight, length, head circumference, and diagnoses at time of discharge, routinely-ordered discharge brain MRI findings
- 6. Neurodevelopmental assessment:

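### The food-efficiency window can lengthen with illness and feeding after randomisation; a fixed 14-day window would remove a small, avoidable risk of bias

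*Combined protocol and SAP*

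**What the plan says.** The combined protocol and SAP describes the window for food efficiency in several places.

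- **Secondary Aims, item 1:** the aim is "increased food efficiency (weight gain/calorie intake) during the supplementation period".
- **Data collection, item 3:** the recorded variable is "food efficiency (weight gain divided by caloric intake) while on study supplement".
- **Study supplementation:** L-carnitine is given "intravenously for 2 weeks, and infants randomized to placebo will received 5% glucose" as the comparator. The next paragraph describes the planned supplementation period as two weeks long, but expects that "as many as 10% of the infants in the study will likely continue to rely primarily on parenteral nutrition" beyond it. It attributes withheld feeds to "underlying illnesses such as sepsis or gastrointestinal disorders like necrotizing enterocolitis". For infants below 100 cc/kg/day it says that "carnitine supplementation will be continued until these infant are receiving adequate enteral feeds".
- **Timeline of Assessments, item b:** the supplement ends at two weeks, except that in a small subset "study supplementation will be continued until enteral feeds reach 100 cc/kg/day".
- **Individual Infant Timeline, item 2:** supplement is given within "24 hours of enrollment for total 2 weeks or until enteral intake is at 100 cc/kg/day".

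The Outcome Measures paragraph of Statistical Analyses compares continuous outcomes by unpaired t-test or rank sum test. It does not name food efficiency, set a common window or deal with unequal duration. The intent-to-treat statement under Randomization settles who is analysed, not which days enter the ratio.

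**The concern.** If the ratio is taken over all days on supplement, its numerator and denominator span two weeks in most infants and longer in some. The extra days belong to a different stage of growth, so an infant's value can move for reasons unrelated to how well calories are used.

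The length is also fixed after randomisation, by illness and feeding tolerance, and treatment might influence it. The section on systemic effects reports a lower rate of proven infection with carnitine in the group's previous trial, and sepsis is one of the reasons given for withholding feeds. If fewer carnitine infants were extended, part of any difference in food efficiency would reflect window length.

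The plan's other early growth measures do not have this feature. Percent weight loss is tied to the first two weeks of life, and head growth, in the same sentence as food efficiency, to the first month.

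**Working it through.** The plan gives no mean, SD or sample size for food efficiency, so there is no stated figure to reproduce. The check has three steps.

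**1. Number of infants affected.** The 10% is a ceiling. 0.10 × 100 analysed = 10 infants; 0.10 × 150 recruited = 15.

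**2. Does a longer window alone change the ratio?**

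Inputs from the documents: weight loss 10.8% and regain of birthweight at 11.3 days (Sample size table); supplement start at 72-96 h, i.e. day 3 or 4 (Timeline of Assessments).

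Assumptions not in the documents: regain is counted from birth; lowest weight on day 4-6; growth after regain of 10-20 g/kg/day; constant intake per kg of current weight (100 kcal/kg/day, which cancels in relative change).

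Ratio = [w(end) − w(start)] ÷ [intake × area under w from start to end], with w as a fraction of birthweight: linear down to the lowest point, linear up to day 11.3, then exponential.

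Example with start day 3, lowest weight day 5 and growth 15 g/kg/day:

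- w(3) = 1 − 0.108 × 3/5 = 0.9352.
- Area from day 3 to 11.3 = 1.827 + 5.960 = 7.787.
- 14 days (to day 17): w = exp(0.015 × 5.7) = 1.0893. Gain = 154.1 g per kg birthweight. Area = 7.787 + 0.0893/0.015 = 13.74. Ratio = 154.1/1374 = 0.112 g/kcal.
- 28 days (to day 31): w = exp(0.015 × 19.7) = 1.3438. Gain = 408.6 g. Area = 7.787 + 0.3438/0.015 = 30.71. Ratio = 408.6/3071 = 0.133 g/kcal.
- Change = 0.133/0.112 − 1, or +18.7% before rounding, on an identical growth path.

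Over the whole grid of assumptions, relative to 14 days:

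| Window | Change in ratio |
|---|---|
| 21 days | −8% to +22% |
| 28 days | −12% to +33% |
| 42 days | −16% to +44% |

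Dividing by calories therefore does not cancel duration, but even the direction depends on the assumptions. The Individual Infant Timeline wording could also be read as allowing an earlier end. On that reading, a 7-day window changes the ratio by −51% to +10% (lowest weight fixed at day 5).

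**3. Effect on the arm comparison.** Bias in SD units = difference in extended proportion × relative shift ÷ coefficient of variation. The extension rates, the shift and a coefficient of variation of 0.2-0.4 are all assumptions. Rejection rates are for a two-sided 0.05 t-test at 50 per arm with no true effect (noncentral t, 98 df, noncentrality = bias × √25).

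| Extended, by arm | Shift | Bias, % of mean | Bias, SD | Rejection |
|---|---|---|---|---|
| 10% vs 10% | any | 0 | 0 | 5.0% |
| 5% vs 15% | ±10% | 1.0 | 0.025-0.05 | 5.2%-5.7% |
| 5% vs 10% | ±30% | 1.5 | 0.037-0.075 | 5.4%-6.6% |
| 5% vs 15% | ±30% | 3.0 | 0.075-0.15 | 6.6%-11.5% |

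As a cross-check, a shift of 1 SD with a gap of 5-10 percentage points gives 0.05 × 1 to 0.10 × 1 = 0.05-0.10 SD. A 30% shift is a severe case: the grid does not reach it at 21 days and reaches it only at its upper end at 28.

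**The case against.** The best counter-argument is that the window may already be fixed. The Study supplementation section describes the planned period as two weeks, with continued parenteral nutrition lying beyond it, so the phrase in the secondary aim may mean those two weeks. That reading is possible. It conflicts with Data collection item 3, which links the ratio to being on supplement, and a data manager following that item would include the extra days. The ambiguity stands.

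Several stronger readings are tempting but unsupported:

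- **That the comparison is biased as planned.** Equal extension gives no bias in the mean difference. Staff are blinded and nutrition follows the standard unit protocol. The infection finding is unpublished and comes from a study that the protocol says was not powered for it. It makes a difference in extension plausible, not expected.
- **That only the carnitine arm is extended.** One sentence mentions only carnitine, but it concerns study patients generally, and the Timeline of Assessments refers to the study supplement. With blinded staff, extension in both arms is the natural reading.
- **That the first 14 days are nearly all loss and regain.** Fourteen days from day 3 or 4 end on day 17 or 18, which is 5.7-6.7 days past the mean regain at day 11.3.
- **That extension is unlimited.** It ends at 100 cc/kg/day; what is missing is a maximum number of days.

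It is also fair to say that a fixed window does not deal with deaths inside it, and does not remove the effect of sepsis or necrotizing enterocolitis on weight gain itself.

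**Conclusion.** The point holds as a minor one. Read with the data-collection item, food efficiency covers different days in different infants, and the length depends on events after randomisation. Bias needs a difference in extension between arms, and nothing in the documents shows that one will occur. If it did, the bias would be roughly 0.05-0.15 SD under the larger assumptions above and smaller under milder ones. Those figures rest on assumed extension rates, an assumed shift and an assumed coefficient of variation; only the 10% ceiling, the weight-loss and regain figures and the start time come from the plan.

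The outcome is half of one secondary aim, is absent from the power table, and shares its window with no primary outcome. A precise definition is worth having because it costs little.

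**What to change.** This changes the analysis definition only; no infant's treatment and no sample size changes.

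1. Define food efficiency as weight change divided by total caloric intake over the first 14 days from first study supplement, in every randomised infant included in the analysis, whatever the actual duration of supplementation. The part of any difference due only to window length is then zero by construction.
2. State which weight closes the window: the nearest recorded weight, or interpolation between the weights on either side. Data collection item 4a has weights going from daily to weekly once birthweight is regained, on average before day 17-18 of life.
3. State how deaths and transfers before day 14 are handled. The protocol expects substantial mortality in the youngest infants.
4. Report the on-supplement ratio as supportive only, with supplementation duration and the proportion extended by arm.
5. Reconcile the descriptions of the supplementation period in Secondary Aims, Study supplementation, Timeline of Assessments, Individual Infant Timeline and Data collection, including whether carnitine or study supplement is meant.

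The cost is a few sentences. Caloric intake is already collected, though the case report form should allow it to be totalled to day 14. The small downside is that the closing weight is approximate or interpolated in infants already on weekly weights.

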 - o potentially life-threatening congenital anomaly
 - o known hereditary metabolic disorder
 - o known chromosomal abnormality
 - teratogen exposure with symptomatic substance withdrawal
 - o congenital viral infections
 - microcephaly
 - Grade IV intraventricular hemorrhage (IVH) or seizures documented within first 72 hours of birth
 - Critically-ill with life expectancy less than 72 hours
 - Unable to obtain consent within 72 hours of birth
 - Enrolled in another intervention trial

Participant recruitment: Parents or guardians of infants who meet study criteria will be approached regarding the study as early as possible within 72 hours of the infant's birth. Informed consent will be obtained by study investigators and coordinators. Permission will be requested to re-contact the families after completion of the supplementation study for follow-up.

Randomization: As previously described by Pande et al., enrolled patients will be randomized to either the treatment group (L-carnitine, 50 µmol/kg/day) or placebo group (5% glucose, similar volume as the L-carnitine group).²⁸ Patients who meet study entry criteria and have signed informed parental/guardian consent will be enrolled in the study. Because gestational age and small for gestational age (SGA) status will impact our outcome measures, we will ensure they are equally distributed in the arms of the study by stratifying based upon these variables. We will analyze the two study arms using an intent-to-treat analysis. Therefore, enrolled patients will be stratified into fourgroups: gestational age 23 to 26 6/7 weeks, gestational age 27 to 29 6/7weeks, gestational age 30 to 31 6/7 weeks and small for gestational age (SGA). Patients within each stratum will be randomized by the pharmacist using a computerized block-generation with sets of 4. In the case of multiple births, all infants must meet study criteria, and the infants will be randomized as a set. One infant of the multiple-birth set will be randomly chosen for inclusion in the analysis. A recruitment log of all screened infants will be maintained. Clinicians and the nursing staff will be unaware of the arm of the treatment protocol to which the patient is assigned. Codes will be unblinded only after all patients have reached the study end-point, or at the request of the Data Safety Monitoring Board.

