 enrollment and at the end of the intervention (and again if a blood transfusion is administered within this period) 5. Amplitude-integrated EEG readings – within 2-3 of study enrollment and at 28, 32, 36 and 40 weeks' post-menstrual age (dashed lines) 6. Hearing screens – OAE and BAER during the NICU course 7. Brain MRI at 36-40 weeks' GA 8. NNNS at term-equivalent follow-up visit 	3.	(Growth parameters, fluid and nutrition intake and important hospital events), also includes interview with mother to record demographic		96 hours 2 weeks
 study enrollment and at 28, 32, 36 and 40 weeks' post-menstrual age (dashed lines) 6. Hearing screens – OAE and BAER 6. Hearing screens – OAE and BAER 7. Brain MRI at 36-40 weeks' GA 8. NNNS at term-equivalent follow-up visit 	4.	enrollment and at the end of the intervention		28 weeks
during the NICU course 30 week 7. Brain MRI at 36-40 weeks' GA NICU Discharge 8. NNNS at term-equivalent follow-up visit Term-equivalent	5.	study enrollment and at 28, 32, 36 and 40 weeks'		32 weeks
8. NNNS at term-equivalent follow-up visit	6.	• •		36 weeks
	7.	Brain MRI at 36-40 weeks' GA		NICU Discharge
	8.	NNNS at term-equivalent follow-up visit	· ·····	Term- equivalent (due date)
	9.	corrected ago		18-24 months CGA

Serum carnitine profiles: Blood samples (dried blood spots) will be collected at study enrollment and again at two weeks of lifefor measurement of acylcarnitine profiles as well as total and free carnitine levels. Collected samples will be batched and shipped to Baylor College of Medicine. As blood transfusions may impact carnitine levels, these studies will be drawn prior to a blood transfusion required between the first and second weeks of life.

Study specimens will be stored and used for future research purposes provided parents give consent for the storage and future use of the samples. Clinical information will be linked to the study specimens.

Data collection: After study enrollment, medical history and baseline data will be collected for each infant enrolled in the study. Prospective data will be recorded on a weekly basis throughout the NICU stay and after discharge at specific time points. Data will be recorded on standardized case report forms (CRFs) organized into the following categories:

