The effect of L-carnitine supplementation on outcome measures in enrolled infants will be examined for significance by comparing the two groups using unpaired data analysis with the assistance of a statistician. Continuous data (percent weight loss, time to regain birthweight, NNNS score, BSID-III scores) will be compared between the "placebo" and the "carnitine supplemented" groups by unpaired student t-test (a 2 tailed P value <0.05 will be considered to indicate statistical significance) or Wilcoxon's rank sum test for non-parametric parameters. Unmatched nominal data will be compared using Fisher's Exact Test or Chi-square test as required (e.g.: presence or absence of normalization of the carnitine profile; or presence or absence of pathological findings on the discharge MRI). Logistic regression models will be used to adjust for potentially confounding factors including gestational age, birth weight, race, gender, Apgar scores.

Risks and Discomforts:

A brief description of the risks and discomforts associated with this study is included in the protocol consent form and will be discussed in detail with each family at the time of study enrollment.

Carnitine is routinely administered with parenteral nutrition in approximately one-third of the neonatal intensive care units in the United States, although not in the Jack D. Weiler Hospital or Montefiore North Division NICU's. Carnitine is FDA-approved, and there have been no reports of severe toxicity from

overdose. Data available from the adult literature reports side effects of mild gastrointestinal symptoms such as gastritis, vomiting, diarrhea or abdominal cramping; body odor; and seizures, in patients with or without a known seizure disorder. These side effects are dose-dependent and might be avoided by slow consumption of the solution or greater dilution. One investigator reported transient elevation of triglycerides and increased platelet aggregation in uremic patients with severe renal insufficiency who received high doses of carnitine supplementation.⁵²

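### Carnitine is measured as a quantity at enrolment and follow-up, but the only analysis named is a yes/no normalization whose reference is not defined

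*Combined protocol and SAP*

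**What the plan says.** Secondary Aims, item 2, asks whether the carnitine profile has become normal by two weeks of age, "compared with infants born at a post-menstrual age 2 weeks later". The Inclusion criteria admit "Infants born <32weeks' gestation", and under Randomization the oldest gestational-age stratum runs from 30 0/7 to 31 6/7 weeks.

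The Serum carnitine profiles section says that blood spots "will be collected at study enrollment and again at two weeks of lifefor measurement". What is obtained is "measurement of acylcarnitine profiles as well as total and free carnitine levels", so the raw data are quantities and a pre-supplement value is planned for each infant.

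Outcome Measures gives carnitine as an example of nominal data, "presence or absence of normalization of the carnitine profile", to be tested by Fisher's exact or chi-square. The outcomes listed there as continuous are the BSID-III and NNNS scores, weight loss and time to recover birthweight; carnitine is not among them. The logistic models adjust for Apgar scores, gender, race, birth weight and gestational age, but not for the enrolment carnitine level. No section names a reference population, a reference range, the analyte that decides normalization, or a cut-off.

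**The concern.** The carnitine panels are the plan's only measurement of the supplemented substance itself. If the primary outcomes show no effect, these panels separate two explanations: levels did not rise, or they rose without benefit. Two features weaken the panels for that purpose.

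- Cutting a measured level to yes/no loses information, and leaving out the enrolment level loses more.
- The classification cannot be carried out from the text. With the analyte, cut-off and reference group all open, normalization could be defined in several ways after the data are seen. The gap applies to every stratum. It is plainest for infants born at 30 weeks or later, because the trial enrols nobody who could serve as their later-born comparators.

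**Working it through.** **Reference group.** Add 14 days to each gestational-age stratum and compare with the enrolment limit of under 32 weeks:

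| Stratum at birth | Comparator needed | Gestational-age days inside the trial range |
|---|---|---|
| 23 0/7 to 26 6/7 | 25 0/7 to 28 6/7 | 28 of 28 |
| 27 0/7 to 29 6/7 | 29 0/7 to 31 6/7 | 21 of 21 |
| 30 0/7 to 31 6/7 | 32 0/7 to 33 6/7 | 0 of 14 |

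Infants in the SGA stratum born at 30 weeks or later are in the same position as the last row. For all of these, the reference has to come from outside the trial.

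**The plan's own figure.** The plan states no power for carnitine. Its one power statement, for the primary outcomes, is 0.80 at 0.5 SD with 50 per arm. A two-sided t-test at 0.05 gives 0.697; 0.80 is reached only one-sided. That mismatch is a separate matter. The two-sided 0.70 is the baseline used here.

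**Inputs.** From the documents: 50 per arm and two-sided 0.05. Assumed: normal data and a shift of d SD between arms. The 0.5 SD value is borrowed from the primary outcomes, so larger shifts are shown as well.

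**Formulas.**
- Continuous level: noncentral t with noncentrality d × √(n/2) and 2n − 2 degrees of freedom. At d = 0.5 and n = 50 this is 0.5 × √25 = 2.5 on 98 degrees of freedom.
- Yes/no, cut at the pooled median: proportions Φ(−d/2) and Φ(d/2), with power by enumerating all pairs of binomial counts.

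| Shift | Proportions | t-test | Chi-square | Fisher |
|---|---|---|---|---|
| 0.5 SD | 40.1% vs 59.9% | 0.70 | 0.53 | 0.45 |
| 0.8 SD | 34.5% vs 65.5% | 0.98 | 0.90 | 0.86 |
| 1.0 SD | 30.9% vs 69.1% | 0.999 | 0.98 | 0.97 |

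A cut away from the middle costs more. At 0.5 SD, with the cut 1 SD above the placebo mean (15.9% vs 30.9%), chi-square power is 0.43 and Fisher 0.35.

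**Adjusting for the enrolment level.** With correlation r between enrolment and follow-up levels, the effective shift is d/√(1 − r²). The documents give no r. At d = 0.5:
- r = 0.3: 0.524, power 0.74
- r = 0.5: 0.577, power 0.82
- r = 0.7: 0.700, power 0.93

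**Which sample.** Secondary Aim 2 and the Serum carnitine profiles section place the follow-up panel by age, at two weeks of life. The Timeline of Assessments counts two weeks from the start of the study, and the supplement itself starts at 72 to 96 hours. Fourteen days from that start is about day 17 to 18 of life (3 + 14 to 4 + 14). The Individual Infant Timeline ties the panel to the end of the intervention, which is later still in infants whose supplement is continued. Draws before a transfusion in the second week add a further candidate sample. These statements do not identify one follow-up value per infant.

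**The case against.** The strongest reply has four parts.

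- **Randomisation is intact.** A reader might infer that judging infants against a later-born group abandons the randomised comparison. It does not. Outcome Measures compares carnitine with placebo; the later-born infants only define who counts as normal, as any reference range would. This stands in full.
- **No stratum is excluded.** A reader might also infer that infants born at 30 weeks or later drop out of this outcome. The aim does not say that comparators must be trial infants, and an external reference could serve. What remains is that none is named, for these infants or any others.
- **Normalization is its own question.** The background argues that physiologic dosing may balance deficiency against excess, so a higher mean is not automatically better and a comparison of means cannot show whether a target was reached. This is a good reason to keep the binary outcome. It does not argue against adding the continuous one. The plan gives normalization only as an example, so a continuous analysis is not ruled out, but none is specified.
- **The power loss may be small.** Supplementing the measured substance could move it by far more than 0.5 SD, and at 1.0 SD the loss is slight. Fifty per arm is also the number left after attrition over the whole study; at two weeks up to 75 per arm might have panels, giving 0.86 (t-test), 0.70 (chi-square) and 0.65 (Fisher) at 0.5 SD. This stands, and is why the loss is given as a range.

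**Conclusion.** The point holds as a gap in specification and an avoidable loss of information in a secondary outcome. No primary outcome depends on it.

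That the reference is undefined, and that trial infants cannot supply it for births at 30 to 31 6/7 weeks, follows from the text at any effect size. The power loss is conditional. Under the stated assumptions it runs from 0.70 down to 0.53 or 0.45 at a 0.5 SD shift, to almost nothing at 1.0 SD. The gain from enrolment adjustment likewise rests on an assumed correlation.

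The documents do not support demoting normalization to a description or limiting it to infants born before 30 weeks. The limit would itself remove randomised infants from the comparison.

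**What to change.** 1. Add to Outcome Measures a between-arm comparison of follow-up free and total carnitine as continuous values (log scale if skewed), adjusted for the enrolment level and the randomisation strata. Name it as the test of whether supplementation changed carnitine.
2. Keep normalization as a between-arm outcome in all strata, judged against one reference fixed before unblinding, with its source, analyte and cut-off stated. The reference must cover 32 to 33 6/7 weeks.
3. State which follow-up sample counts for each infant, reconciling the age-based timing with the timings counted from study start and from the end of the intervention, and saying how pre-transfusion draws are used.

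The cost is a little more analysis work, the choice of a reference, and one more secondary analysis to report. Both panels are already planned, so no additional blood, visit or infant is needed.
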